We will therefore secondarily conduct an economic evaluation to determine the relative incremental hospital cost of each fluid. To the extent that one fluid or the other reduces cost (assuming similar complication rates), the Clinic will be able to reduce cost by specifying the appropriate fluid without impairing quality.

Evidence that one fluid or the other causes few complications would be a strong quality indicator that the Clinic should standardize perioperative fluid selection.

Outcomes

1. **Primary:** Post-operative morbidity, as assessed by a composite outcome consisting of the following major complication components: renal, respiratory, infectious and hemorrhagic.
2. **Secondary:**
 - a. Acute kidney injury (AKIN criteria);
 - b. Economic evaluation.
3. **Tertiary:**
 - a) Blood transfusion;
 - b) Number of plasma electrolytes determinations;
 - c) Electrolyte replacement (i.e., administration of calcium, magnesium, potassium, or bicarbonate);
 - d) Post-operative nausea vomiting.
 - e) Myocardial Injury after Noncardiac Surgery
 - f) Cardiac complication

Methods

We propose an alternating intervention quality study comparing intraoperative fluid management with normal saline and lactated Ringer's solutions. This general approach to quality questions has been used at the Clinic and shown to produce more reliably clinical guidance than propensity-matched retrospective analyses.³⁷

This project will focus on colorectal and orthopedic surgery because these operations are conducted in physically distinct units that are normally staffed by small groups of anesthesiologists. Furthermore, most of the cases are substantial and require postoperative hospitalization. Both the anesthesia and surgical teams have agreed to the proposed project and representatives are co-investigators.

Protocol

We propose that all orthopedic and colorectal surgery operating rooms will alternate between using either normal saline or lactated Ringer's solution for 2-week periods. For example, the first period will use normal saline; the second will use lactated Ringer's, and so on for a maximum total of approximately 36 cycles. Thus, fluid choice will not be randomized on a per-patient or even per-period basis. Patients will not be informed of their group assignments, but will be told what fluids they received in the event they ask.

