Because the incidence and severity of the individual major complications vary considerably, we will analyze morbidities in a multivariate (one record per outcome per patient) analysis instead of a collapsed composite approach. A multivariate approach allows us to capture information regarding individual morbidities and the correlation between morbidities.

The average relative effect of lactated Ringer's solution versus saline will be assessed across the five categories of major complications using generalized estimating equations (GEE) 'distinct effects' model with an unstructured working correlation matrix.⁵¹ To assess heterogeneity of the fluid effect across components of the primary outcome, we will assess the treatment-by-component interaction in a distinct effects GEE model. We will assess whether the average component-specific treatment effect was equal to zero using an average relative effect test. However, if the baseline incidences are either quite different from each other or if some are very small (say < 1%), will instead use the common effect GEE test. All analyses will adjust for unbalanced potentially confounding baseline characteristics.

Secondary analysis

The economic evaluation will be conducted from the hospital/payer perspective to determine the optimal strategy for economic outcomes between the two interventions. The evaluation will determine the incremental costs between the two interventions; uncomplicated care and care of complications, as well as a combined incremental cost. An example analysis is listed below showing the incremental difference between the interventions for various outcomes for standard care and complications. A cost is assigned to each outcome and a total cost per patient calculated.

Standard Care - Example

	Intervention A	Intervention B	Incremental Dif.	Estimated Cost	Total Cost
LOS	1	0.8	0.2	100	20
Electrolyte Measures	10	8	2	10	20
Electrolyte Replacement	2	1	1	20	20
				Total Cost/pt	60

Complications - Example

	Intervention A incidence	Intervention B incidence	Incremental Dif.	Estimated Cost	Total Cost
MI	0.1	0.05	0.05	10,000	500
DVT	0.2	0.1	0.1	1000	100
Pneumonia	0.3	0.2	0.1	2000	200
				Total Cost/pt	800

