This study is designed to have about 90% power at the 0.05 significance level to detect a 20% relative decrease in major complications LR versus saline. We estimated the incidence of complications in the control group (saline) assuming that the two groups average out to the overall incidence. Sample size was calculated assuming a conservative correlation of 0.3 between outcomes. We estimated sample size using the MULTBINPOW SAS macro, which can estimate power for average relative effect GEE models given varying correlations and sample sizes (Mascha EJ Power Calculations for Tests on a Vector of Binary Outcomes (MULTBINPOW)).⁵¹ Cleveland Clinic Statistical Software Series 10 edn Cleveland; 2011: SAS program uses simulations to compute and display comparative power of several parallel-group multivariate tests for treatment effect on a vector of binary events.⁵² After accounting for 3 interim analyses and 1 final analysis, we will need to enroll a maximum of 8,548 patients for this study. If the Average Relative Effect analysis proves insufficient, we expect to nonetheless have > 99% power to detect a 20% relative increase in major complications in saline versus LR using either the collapsed composite or common effect GEE methods.

However, it is likely that the study would stop early. The table below provides boundary crossing probabilities for possible true underlying treatment effects: Null (no effect), Alternative (20% relative increase), half-way between the null and alternative, and 1.5 times the alternative effect. If the alternative hypothesis were true, the probability of crossing either the efficacy or futility boundary would be a cumulative 40% and 78% at interim analyses 2 and 3 (see “Alternative” row). Thus, there would be a 40% chance of stopping the study after N = 3,420 patients and 78% chance when N = 6,668 patients were enrolled if the alternative hypothesis is true. With an estimated 6,240 eligible patients available every year, we can expect this study to take a maximum of 1.37 years.

Expected Cumulative Boundary Crossing Probabilities (i.e., boundary crossing probabilities for either efficacy or futility)					
Effect*	Expected Crossing Stage	Boundary Crossing Probabilities			
		Interim 1	Interim 2	Interim 3	Final
Null	2.7	0.08	0.42	0.84	1.0
Alternative	2.7	0.09	0.40	0.78	1.0
½ Null, Alternative	3.0	0.06	0.28	0.63	1.0
Alt x 1.5	1.9	0.29	0.81	0.98	1.0

* True treatment effect in the population

Internal pilot study

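### Fluid is assigned by about 36 alternating 2-week periods, but analysis and sample size treat patients as independent, so the stated 5% alpha and about 90% power are not assured

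*Protocol*

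**What the plan says.** **Assignment.** Under Methods, Protocol, all rooms in both services "will alternate between using either normal saline or lactated Ringer's solution for 2-week periods". The section continues "and so on for a maximum total of approximately 36 cycles" and states that "fluid choice will not be randomized on a per-patient or even per-period basis". The same section lets clinicians use another fluid if clinically indicated, so the period fixes the assigned fluid but not always the fluid received.

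**Primary model.** The Primary analysis section states "we will analyze morbidities in a multivariate (one record per outcome per patient) analysis instead of a collapsed composite approach". It specifies a "generalized estimating equations (GEE) 'distinct effects' model with an unstructured working correlation matrix" across five components. It switches to a common effect test if component incidences differ widely or some are very small, for example below 1%.

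**Other models.** Tertiary outcomes analysis, which also covers AKIN stage, uses proportional odds, logistic, and Poisson or negative binomial regression with propensity weights.

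**Sample size.** The only correlation allowed for is between outcomes: "Sample size was calculated assuming a conservative correlation of 0.3 between outcomes". The maximum is 8,548 patients for about 90% power at the 0.05 level, with four looks.

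The protocol contains no period term, ICC, design effect or period-level variance.

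**The concern.** When a whole calendar period is assigned to one arm, anything shared by the patients of that period and not captured by covariates enters the treatment contrast. Examples are a cluster of infections, a staffing change or a shift in recording. That variance shrinks with the number of periods, not with the number of patients. A standard error built on independent patients leaves it out.

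Two features of the plan might seem to cover this but do not. The unstructured working matrix describes correlation between the outcomes of one patient, not between patients of one period. Propensity weighting balances measured patient characteristics but adds no between-period component to the variance.

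At stake are all four boundary comparisons, the confidence intervals and the power statement. The protocol intends the result to support standardising fluid choice. The matter is not simply left to a statistical analysis plan, because the protocol itself fixes the model, its correlation structure, the boundaries and the sample size.

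**Working it through.** **1. Number and size of periods.** "With an estimated 6,240 eligible patients available every year, we can expect this study to take a maximum of 1.37 years". 8,548 / 6,240 = 1.37 years, and 1.37 × 26 = 35.6 two-week periods. The 36 cycles are therefore single periods, not saline/Ringer's pairs. Patients per period: m = 8,548 / 36 = 237.

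**2. The plan's own figures.** Two-sided gamma(-4) spending at four equally spaced looks gives 0.00160, 0.00483, 0.01471 and 0.0440. The Interim analyses section prints 0.00160, 0.00482, 0.01472 and 0.04404, so the boundaries reproduce apart from rounding.

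The 8,548 does not reproduce. A Wald calculation for the mean log odds ratio with independent patients, the stated saline rates, a 20% reduction, 90% power and correlation 0.3 gives 18,875. Multiplied by 1.138 for the interim looks, this is about 21,500. At correlation 0 it is 9,942 × 1.138, about 11,300. The simulation settings are not all given, and 0.3 exceeds the largest feasible correlation of infection with each other component (0.13 to 0.29). This is therefore no proof of an arithmetic error and is a separate matter. It does show that 8,548 hides no visible margin for a design effect.

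**3. Independent period shocks.** The ICC is an assumption. The infectious component has incidence p = 0.2376 (Sample size table).

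- SD of the true period rate = √(ICC × p × (1 − p))
- Design effect DE = 1 + (m − 1) × ICC = 1 + 236 × ICC
- True alpha = 2 × (1 − Φ(1.96/√DE))
- Power of a valid test = Φ(3.2415/√DE − 1.96), where 3.2415 = 1.96 + 1.2815 corresponds to 90% power

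| ICC | SD of period rate | DE | True alpha | Power |
|---|---|---|---|---|
| 0 | 0 | 1.00 | 5.0% | 90% |
| 0.001 | 1.3 points | 1.24 | 7.8% | 83% |
| 0.002 | 1.9 points | 1.47 | 10.6% | 76% |
| 0.005 | 3.0 points | 2.18 | 18.4% | 59% |

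Simulation of 36 alternating periods of 237 patients under no effect agrees: the patient-level test rejects 7.8%, 10.6% and 18.5%. A period-level t-test with 34 degrees of freedom stays at 4.9 to 5.3%.

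**4. Slowly drifting period effects.** If neighbouring periods resemble each other with lag-1 autocorrelation ρ, alternation multiplies the between-period part by about (1 − ρ)/(1 + ρ), so DE ≈ 1 + 236 × ICC × (1 − ρ)/(1 + ρ). The value of ρ is also an assumption.

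| ICC | ρ = 0.5 (factor 1/3): simulated; formula | ρ = 0.9 (factor 0.0526): simulated; formula |
|---|---|---|
| 0.001 | 5.6%; 5.9% | 5.1%; 5.1% |
| 0.002 | 7.1%; 6.9% | 5.4%; 5.3% |
| 0.005 | 9.7%; 9.7% | 5.7%; 5.7% |

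The small differences are simulation error and the approximation in the formula.

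**5. Which primary test.** On the planning figures, infection accounts for 2,895 of 65 + 213 + 285 + 2,895 + 311 = 3,769 component events, or 77%. In-hospital mortality is 0.53%, below the example threshold of 1%, so the switch to the common effect test is likely. That test is dominated by infection. Assume the same log-odds period variance in every component, independent shocks and a within-patient correlation of 0 to 0.3. At infection ICC 0.001, 0.002 and 0.005 the true alpha is then:

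- common effect test: 6.2–8.9%, 7.4–12.8% and 11–23%
- average relative effect test: 5.1–6.1%, 5.2–7.3% and 5.6–10.8%

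The second test is less affected because it weights the rare components equally, and their sampling variance dominates.

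**6. Interim 1.** 8,548 / 4 = 2,137 patients, and 2,137 / 240 (from 6,240 / 26) = 8.9 periods. The first look, with its 0.00160 boundary, would rest on about five periods of one fluid against four of the other.

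**The case against.** The strongest reply is that nothing in the protocol shows the within-period correlation to be above zero. Weighting on observed confounders and adjusting for residual imbalance remove part of the case-mix variation. Small, stable anesthesia groups limit staffing variation. Season and gradual coding change are shared by adjacent periods, so alternation largely cancels them. All of this stands, and it lowers the plausible inflation. None of it supplies a between-period variance or rules out period-specific shocks.

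A reader might infer more than the protocol supports:

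- **That the 5% level is known to fail, or that alpha is 18%.** The ICC is not given, and 18.4% is the independent-shock end of the range for one component in a single-look test. It is not the four-look error rate of the planned primary test.
- **That all patients in a period receive the same fluid.** Clinicians may deviate, so only assignment is by period.
- **That the period within each surgical unit should be the cluster.** All rooms switch together, so shocks common to both units would be missed.

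Degrees of freedom and exact covariate lists are commonly left to an analysis plan. The choice of the patient as the independent unit is not open here, because the protocol has made it.

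**Conclusion.** The point holds conditionally. Assignment is by about 36 calendar periods, while the primary model, the tertiary models, the boundaries and the sample size use the patient as the independent unit. The stated 5% type I error and about 90% power are therefore not assured if outcomes vary between periods beyond the measured covariates.

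Over assumed ICCs of 0.001 to 0.005, the true alpha for the infectious component in a single look runs from barely above 5% under strong drift to about 18% under independent shocks. The corresponding power under independent shocks is 83% down to 59%. Inflation is smaller for the average relative effect test and nil at ICC zero. It merits correction before analysis, because a period-to-period SD of only 1.3 points around a 23.8% infection rate is enough to move 5% to about 8% if shocks are independent.

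**What to change.** 1. In all primary, secondary and tertiary models, make the calendar 2-week period common to both units, or the consecutive saline/Ringer's pair, the cluster for the empirical variance. Outcomes within a patient are then nested inside that cluster.
2. Apply a small-sample correction with degrees of freedom from the number of periods (36 − 2 = 34 at the maximum) or pairs (18 − 1 = 17). Include surgical unit and calendar time as covariates. Pairing or a time term matters because an unpaired period-level variance counts drift that alternation has already cancelled and would be conservative.
3. Hold each interim at the end of a completed pair, and recompute the boundaries from the same spending function if the information fractions move.
4. Restate power over a range of ICC, including zero, without enrolling more patients.

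**Cost.** Intervals become somewhat wider and the stated power less favourable. The first interim would have few degrees of freedom: four completed pairs give 3 on a pair basis, or 8 − 2 = 6 on a period basis. Stopping there becomes less likely. If the ICC is close to zero, little is lost at the final analysis.

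Randomising the fluid order within pairs would strengthen the design, but it is an optional design change and not part of this correction.

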We will use an overall alpha of 0.05 for both the primary and secondary/tertiary analyses, using a significance criterion of 0.05 for the primary analysis and 0.006 for each secondary/tertiary analysis (i.e., 0.05/8; Bonferroni correction). SAS Version 9.3 (SAS Institute, Cary, NC, USA) and R statistical software version 2.15.3 (R Project for Statistical Computing, Vienna, Austria) will be used for the analyses.

Pilot patients

We will enroll at least 5 pilot patients to test the feasibility of protocol adherence and data collection.

Interim analyses

At each quarter of the maximum enrollment (8,548), we will conduct an interim analysis to assess for efficacy and futility of using lactated Ringer's solution versus saline on our composite of major complications. The interim analysis will use the gamma spending function with parameters -4 for alpha (efficacy) and -1 for beta (futility). Boundaries for efficacy (futility on parentheses) at each stage are $P \leq 0.00160$ ($P > 0.92646$), $P \leq 0.00482$ ($P > 0.62368$), $P \leq 0.01472$ ($P > 0.2011$), and $P \leq 0.04404$ ($P > 0.04404$), respectively.

Sample size

Based on a preliminary query of the PHDS database, we found the incidence of complications among all patients who would have met the inclusion/exclusion criteria for this study:

Outcome	No. Missing	Overall Incidence (%)	Estimated Saline
----------------	--------------------	------------------------------	-------------------------

		(N = 12,182)	Incidence (%)
In-hospital mortality	0	65 (0.53)	0.59
Renal (AKI classification > 1)	0	213 (1.75)	1.94
Respiratory	90	285 (2.34)	2.60
Infectious	83	2895 (23.76)	26.40
Hematologic	83	311 (2.55)	2.83

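### The protocol states two significance criteria for the primary test, 0.05 and a final-look boundary of 0.04404, and does not say that 0.05 is only the overall level

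*Protocol*

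**What the plan says.** Three places in the protocol bear on the criterion for the primary test.

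- **Last paragraph of Tertiary outcomes analysis.** It opens with "We will use an overall alpha of 0.05 for both the primary and secondary/tertiary analyses" and continues "using a significance criterion of 0.05 for the primary analysis". It pairs this with "0.006 for each secondary/tertiary analysis (i.e., 0.05/8; Bonferroni correction". The paragraph does not mention interim looks.
- **Interim analyses.** "At each quarter of the maximum enrollment (8,548), we will conduct an interim analysis to assess for efficacy and futility", with the composite of major complications as the outcome. "The interim analysis will use the gamma spending function with parameters -4 for alpha (efficacy) and -1 for beta (futility"). The efficacy boundaries are 0.00160, 0.00482 and 0.01472 at looks 1 to 3, and the list ends "and $P \leq 0.04404$ ($P > 0.04404$), respectively". The section does not say how 0.04404 relates to 0.05.
- **Sample size.** Power of about 90% is stated at the 0.05 level, and the maximum of 8,548 patients allows for three interim analyses and one final analysis.

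The protocol does not state whether the tests are one- or two-sided, or whether the futility boundaries are binding.

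**The concern.** The first sentence has already named the overall alpha when it goes on to give a criterion. It puts that criterion beside 0.006, which is plainly a cut-off for an individual P value. Read in parallel, 0.05 is also a cut-off for the primary P value. The next section but one gives a different cut-off for the same outcome at the last look.

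The conflict matters for a final P between 0.04404 and 0.05. A value of 0.047, for example, meets the first criterion but lies on the futility side of the second. The choice between them could then be made with the result in view.

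Reaching the last look is realistic. From the protocol's table of boundary-crossing probabilities, the chance of continuing past interim 3 is 1 − 0.78 = 0.22 under the design alternative and 1 − 0.63 = 0.37 at half that effect.

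**Working it through.** **Inputs (Interim analyses).** Looks at t = 0.25, 0.50, 0.75 and 1.00 of 8,548; gamma spending with parameter −4 for alpha; the printed efficacy boundaries; futility at P > 0.92646, 0.62368 and 0.2011 at looks 1 to 3. Overall alpha is 0.05. Two-sided testing is an assumption, checked in step 2.

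**Step 1: alpha spent.** α(t) = 0.05 × (1 − e^(4t)) / (1 − e^4).

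- t = 0.25: 0.05 × 1.7183 / 53.598 = 0.00160
- t = 0.50: 0.05 × 6.3891 / 53.598 = 0.00596
- t = 0.75: 0.05 × 19.0855 / 53.598 = 0.01780
- t = 1.00: 0.05000

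**Step 2: reproduce the printed boundaries.** Recursive numerical integration of the test statistic over four equally spaced looks was used, two-sided and with no credit for futility stopping.

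| Look | Derived P | Printed P |
|---|---|---|
| 1 | 0.00160 | 0.00160 |
| 2 | 0.00483 | 0.00482 |
| 3 | 0.01472 | 0.01472 |
| 4 | 0.04403 | 0.04404 |

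The agreement is within rounding and integration error. If the printed futility boundaries are treated as binding, the final efficacy boundary comes out at about 0.0533. The printed set was therefore built without futility credit. Read as one-sided P values, the printed boundaries total 4.88% by simulation, not 5.00%, which supports the two-sided reading.

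**Step 3: type I error under each final criterion.** The printed interim boundaries are kept. The entries are the probabilities of first crossing the efficacy boundary at each look under the null.

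| Final criterion | Futility | Look 1 | Look 2 | Look 3 | Look 4 | Total |
|---|---|---|---|---|---|---|
| 0.04404 | non-binding | 0.00160 | 0.00435 | 0.01185 | 0.03219 | 0.0500 |
| 0.04404 | always obeyed | 0.00160 | 0.00435 | 0.01162 | 0.02635 | 0.0439 |
| 0.05 | non-binding | 0.00160 | 0.00435 | 0.01185 | 0.03761 | 0.0554 |
| 0.05 | always obeyed | 0.00160 | 0.00435 | 0.01162 | 0.03024 | 0.0478 |

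A simulation of 8 million paths gave 0.0501, 0.0440, 0.0554 and 0.0479 in the same order.

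**Step 4: size.** With non-binding futility, moving the final criterion from 0.04404 to 0.05 adds 0.03761 − 0.03219 = 0.0054, or about half a percentage point. If every futility stop is obeyed it adds 0.03024 − 0.02635 = 0.0039, and the total stays below 5%.

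**The case against.** The strongest reply is that the two figures are compatible. The sentence under Tertiary outcomes analysis can be read as allocating alpha between outcome families: the single primary test keeps the whole 0.05, and the other tests share theirs by Bonferroni. The Interim analyses section then spends that 0.05 over four looks, ending at 0.04404. The arithmetic fits, since the printed boundaries total 0.0500. No sentence says that the final look is tested at 0.05, and a trained statistician would probably apply 0.04404.

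Most of this stands. The boundaries are sound, and this is probably what was meant. It does not settle the wording, however. The sentence gives the overall alpha first and the criterion separately, the matching figure of 0.006 is a per-test cut-off, and neither section refers to the other.

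A reader might go further and infer that the plan breaks its 5% error rate, or that the boundaries were miscalculated. The documents support neither reading. Judged at the printed boundaries, error is controlled at 5%. Even with 0.05 at the last look, error exceeds 5% only if futility is non-binding; with every futility stop obeyed it is about 4.8%. The protocol is silent on which applies. The printed boundaries were built without futility credit, but that does not show that futility stops would be ignored, and the text introducing the crossing-probability table treats crossing either boundary as stopping the study.

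**Conclusion.** The point holds as a conflict in the stated decision rule for the primary outcome. Two criteria are given for one test, and the verdict is undefined for a final P above 0.04404 and up to 0.05. The boundary design is correct and needs no change.

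If 0.05 were applied at the last look, overall two-sided type I error would be about 5.5% with non-binding futility and about 4.8% if every futility stop were obeyed, against 5.0% and 4.4% with 0.04404. These figures assume equally spaced looks and two-sided testing, the latter inferred from the boundaries. The numerical effect is small. The reason to act is that the primary decision rule should not be left to inference.

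**What to change.** Reword the sentence under Tertiary outcomes analysis to say that 0.05 is the overall two-sided alpha for the primary outcome, spent over the four looks. Significance is then judged at P ≤ 0.00160, 0.00482, 0.01472 and 0.04404 at looks 1 to 4, so that 0.04404 and not 0.05 applies at the final analysis. The 0.006 criterion for the other outcomes can stay as written. It would help to add in Interim analyses whether the futility boundaries are binding.

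The change takes one sentence, or two with the futility statement. The boundaries and the maximum enrolment of 8,548 are unaffected. The only cost is a final threshold slightly stricter than 0.05, which the Interim analyses section already specifies.

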Our composite of major complications is a modification of a previously published composite used by Bennett⁴²; similar composites have been used in previous fluid management studies.^{8,43-45} Specifically, we selected major complications that were identified as significant (or near-significant) in one of the largest retrospective analyses comparing normal saline to balanced solution that was based on the Premier database.⁸ Major complications and their associated ICD-9 codes are described in the Appendix.

Secondary outcomes

1. Acute kidney injury (AKIN criteria) :

Risk Injury Failure Loss End stage (RIFLE)⁴⁶ and Acute Kidney Injury Network (AKIN)⁴⁷ criteria are useful tools to assess kidney injury after surgery.⁴⁸ Both criteria are sensitive to kidney injury, but in cardiac surgery⁴⁹, burn⁵⁰ patient's AKIN classification correlated better with mortality than did the RIFLE criteria. We will thus quantify kidney injury with AKIN criteria.

2. Economic evaluation:

The cost of care analysis will incorporate only costs directly relevant to the intervention. The costs for each group will be broken into two components: uncomplicated care (standard care), and care of associated complications.

Costs to be included for uncomplicated care will include LOS, electrolyte management, electrolyte replacement, plasma electrolyte determination, and post-operative nausea and vomiting. Costs to be included for associated complications will include the cost to treat any major complications (Table 3), and blood transfusions.

Costs for each outcome will be sourced from Medicare allowable rates for reimbursement, CC billing data and Elsevier Rx Price Verify Database.

Tertiary outcomes

1. **Blood transfusion:** Number of units transfused during hospitalization of red cells, platelets, and fresh-frozen plasma (each considered separately, Table 5);

2. **Plasma electrolytes determinations:** a count of the number of times blood is drawn for electrolyte determination, for example basic metabolic panel, arterial blood gas analysis, venous blood gas analysis, potassium, magnesium, and calcium determination;
3. **Administration of calcium, magnesium, potassium, or bicarbonate;**
4. **Postoperative nausea vomiting** during PACU (post anesthesia care unit) stay: Postoperative Nursing Progress Record (NPR) - Records nausea vomiting severity as: 0=none, 1= mild, 2=moderate, 3= severe; analysis will compare nausea vomiting (1, 2, 3) to no nausea vomiting (0).

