Using the example results above, results would indicate that using intervention B can save 0.2 days, 2 electrolyte measures and an electrolyte replacement equating to \$60 in savings considering only standard care. Incorporating the potential cost savings from avoiding complications, intervention can reduce the incidence of MI, DVT, and pneumonia equating to a potential cost savings of \$800 per patient. For a hospital performing 1,000 procedures a year, using intervention B would potentially save the hospital \$60,000 in standard care costs and \$800,000 costs from avoiding complications.

Using the methods outlined in the example analysis, the analysis will be performed using the relevant outcomes from the clinical trial. The robustness of the results to changes in variable values will be tested using sensitivity analysis. Sensitivity analysis will include one-way and two-way analyses around the baseline values using the confidence intervals derived from the study. Any values where a confidence interval is unknown including cost variables, a 25% range will be used. Any change in values to which the choice strategy is highly sensitive, further sensitivity analysis will be conducted including threshold analysis.

Tertiary outcomes analysis

We will assess the association between fluids and AKIN classification using a multivariable proportional odds model including propensity score weights and adjusting for unbalanced baseline co-variables as appropriate. If AKIN categories have low incidence, we will combine them and perform a multivariable logistic regression analysis instead.

The association of fluids on blood transfusion will be assessed using separate multivariable Poisson or negative binomial regression models for each transfusion type, as appropriate. We will also assess the association of fluids on plasma electrolytes determination using a multivariable Poisson or negative binomial regression model. The association of fluids with the administration of electrolyte replacement and postoperative nausea and vomiting will be assessed through separate multivariable logistic regression models. All above tertiary analyses will adjust for confounding variables that are unbalanced after propensity score weighting.

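### The 0.05/8 Bonferroni threshold falls at least one test short of the listed secondary and tertiary outcomes, so the claimed overall alpha of 0.05 is not guaranteed

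*Protocol*

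**What the plan says.** The significance criteria stand at the end of the Protocol's Tertiary outcomes analysis section: "We will use an overall alpha of 0.05 for both the primary and secondary/tertiary analyses". The primary analysis is judged at 0.05, and the remaining analyses at "0.006 for each secondary/tertiary analysis (i.e., 0.05/8; Bonferroni correction"). As the primary already uses 0.05, the sentence can only mean a separate 0.05 for the secondary and tertiary family.

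The Outcomes section lists two secondary outcomes (acute kidney injury and an economic evaluation). It lists six tertiary ones: transfusion, number of electrolyte determinations, electrolyte replacement, postoperative nausea and vomiting, "Myocardial Injury after Noncardiac Surgery" (MINS), and cardiac complication.

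Transfusion is defined under Tertiary outcomes as "Number of units transfused during hospitalization of red cells, platelets, and fresh-frozen plasma (each considered separately, Table 5"). The Tertiary outcomes analysis section then models it "using separate multivariable Poisson or negative binomial regression models for each transfusion type". The same section covers kidney injury: "We will assess the association between fluids and AKIN classification using a multivariable proportional odds model". It also gives one count model for electrolyte determinations and one logistic model each for electrolyte replacement and for nausea and vomiting. It names no model for MINS or cardiac complication. The economic evaluation, under Secondary analysis, is described as incremental costs with sensitivity analyses. No hypothesis test is mentioned.

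**The concern.** Bonferroni delivers its stated family error only if the divisor is at least the number of tests performed. The Protocol fixes the divisor at 8, yet its own definitions split one of the eight listed outcomes into three separately tested ones. If the divisor is too small, a secondary or tertiary result just under 0.006 would be declared significant without the error control that the Protocol claims. The family matters because it contains acute kidney injury, the only secondary hypothesis stated under Objectives and Hypotheses.

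**Working it through.** **The plan's own figure.** 0.05/8 = 0.00625, which rounds to the stated 0.006. With eight tests at 0.006 the sum is 8 × 0.006 = 0.048, so the threshold would be valid for eight.

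**Counting the tests**, from the Outcomes, Tertiary outcomes and Tertiary outcomes analysis sections:

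| Outcome | Tests | Basis |
|---|---|---|
| AKIN class | 1 | model stated |
| Transfusion (red cells, platelets, plasma) | 3 | one model per type stated |
| Electrolyte determinations | 1 | model stated |
| Electrolyte replacement | 1 | model stated, taken as any versus none |
| Nausea and vomiting | 1 | model stated |
| MINS | 1 | listed and defined, no model stated |
| Cardiac complication | 1 | listed, no model stated |
| **Total without cost** | **9** | |
| Economic evaluation | 0 or 1 | listed as secondary, no test stated |

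**Family error at the stated threshold.** The Bonferroni bound is m × 0.006. Under independence the error is 1 − (1 − 0.006)^m.

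| m | Bound at 0.006 | Independent tests at 0.006 | Matching threshold 0.05/m |
|---|---|---|---|
| 8 | 0.048 | 0.0470 | 0.00625 |
| 9 | 0.054 | 0.0527 | 0.00556 |
| 10 | 0.060 | 0.0584 | 0.00500 |

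Rounding 0.00625 down to 0.006 therefore does not absorb the extra test. At the unrounded value the bounds are 9 × 0.00625 = 0.05625 and 10 × 0.00625 = 0.0625.

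**Sensitivity to correlation.** The Protocol gives no correlations between these outcomes. I assumed two-sided normal tests with a common correlation, each at 0.006:

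| Assumed correlation | 9 tests | 10 tests |
|---|---|---|
| 0 | 0.0527 | 0.0584 |
| 0.2 | 0.0510 | 0.0563 |
| 0.3 | 0.0489 | 0.0537 |
| 0.5 | 0.0422 | 0.0458 |

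With nine tests the error drops below 0.05 somewhere between correlations of 0.2 and 0.3. With ten it does so between 0.3 and 0.5.

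**The case against.** The best defence of 8 is that only seven tests have a stated model: AKIN 1, transfusion 3, determinations 1, replacement 1, nausea and vomiting 1. Seven at 0.006 sum to 0.042. Adding cost gives eight and 0.048, both within 0.05. On this view MINS and cardiac complication are described but not tested. It is true that their tests are inferred. However, both are listed as tertiary outcomes on the same footing as the others, and the criterion is worded to cover each secondary or tertiary analysis. Leaving them out of the count would leave two listed outcomes with no error control at all.

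The other route to 8 is to count the listed outcomes (2 + 6). That treats transfusion as one test, contrary to its definition and its analysis. The Protocol does not say which route was taken, so a reader should not conclude that the transfusion split in particular was overlooked.

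A reader might also count twelve or thirteen tests by taking calcium, magnesium, potassium and bicarbonate separately. The text does not support this. Replacement is listed as a single outcome, and the separate logistic models distinguish it from nausea and vomiting, not one agent from another.

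Finally, the defence can say that the effect is very small. That stands: for nine tests the threshold moves by about 0.0004, and the primary test, sample size and stopping boundaries do not change.

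**Conclusion.** The divisor is one short of the nine tests that the listed outcomes produce, and two short if cost is formally tested. What is lost is the guarantee: the bound is 0.054 for nine tests and 0.060 for ten, against a claimed 0.05.

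A reader might infer that the true family error exceeds 0.05. That follows only under independence or weak correlation. Transfusion types are plausibly correlated with one another, as are MINS and cardiac complications, and positive correlation could keep the actual error below 0.05.

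The count of nine assumes that every listed clinical outcome is tested, that the three transfusion types are tested separately as written, and that electrolyte replacement is one test. Ten rests on a cost test that the Protocol does not state. This is a small inconsistency in the stated error control for the secondary and tertiary results. It has no bearing on the primary conclusion.

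**What to change.** Add a sentence that lists the tests in the secondary and tertiary family, says whether MINS, cardiac complication and cost are among them, and sets the divisor to match: 0.05/9 = 0.0056, or 0.05/10 = 0.005 if cost is tested.

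Preferably apply Holm's step-down procedure to that list. It controls the same family error under any dependence and rejects at least as often as Bonferroni at the same count. With nine tests the smallest p-value is compared with 0.05/9 = 0.0056, the next with 0.05/8 = 0.00625, then 0.05/7 = 0.0071, and so on.

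Alternatively, test transfusion as a single outcome. The family is then seven, or eight with cost, and the present divisor stands.

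The cost is one sentence and a slightly stricter first threshold. Holm does not fully offset this: a smallest p-value of 0.0058 passes at 0.006 but fails at 0.0056, and Holm would then reject nothing.
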